9.1 Screening

9.1.1 *Visit 1, Day -21*

As shown in [Table 1](#), the following will be performed during Visit 1:

- Obtain informed consent (obtained from the subject prior to any study-related procedures)
- Review and record inclusion and exclusion criteria
- Record medical and seizure history and demographics
- Record vital signs
- Conduct full physical examination (see [Appendix A](#)), including height and weight
- Conduct full neurologic examination (see [Appendix B](#))
- Administer C-SSRS (Baseline/Screening version) (see [Appendix D: COLUMBIA SUICIDE SEVERITY RATING SCALE \(Baseline/Screening\)](#))
- Perform 12-lead ECG once
- Perform serum pregnancy test (female subjects of childbearing potential; if positive, subject will not be enrolled)
- Draw blood for laboratory safety assessment
- Obtain urine for urinalysis

- An MRI or CT scan will be performed during screening if the subject has not had a neuroimaging study within 10 years of Visit 1. This will be used to document the absence of an active brain lesion, and a copy of the report will be made available to the Sponsor
- Include the EEG report in the source document. If an EEG report cannot be obtained, and the subject is otherwise eligible, an EEG may be performed during screening.
- Record concomitant medications
- Schedule Visit 2 to occur within 3 weeks of Visit 1

9.1.2 *Visit 2, Day 1*

All subjects who have not discontinued will be scheduled to appear at the clinic for Visit 2. At Visit 2, subjects who continue to meet all of the inclusion criteria and none of the exclusion criteria will receive study drug.

As shown in [Table 1](#), the following will be performed at Visit 2:

- Review and record inclusion and exclusion criteria
- Record vital signs
- Conduct brief neurologic examination if required (Appendix C)
- Administer C-SSRS (Since Last Visit version) (Appendix E)
- Perform urine pregnancy test (for female subjects of childbearing potential)
- Record concomitant medications
- Record AEs
- For subjects taking phenytoin or phenobarbital, draw blood for phenytoin or phenobarbital trough levels
- For subjects taking concomitant AEDs other than phenytoin or phenobarbital at US sites only, draw blood for concomitant AEDs (oxcarbazepine, topiramate, lamotrigine, lacosamide, clobazam, perampanel and levetiracetam only) levels
- Dispense study drug as instructed by IWRS if all of the inclusion criteria and none of the exclusion criteria are met

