- For subject taking concomitant AEDs other than phenytoin or phenobarbital at US sites only, draw blood for concomitant AED levels (oxcarbazepine, topiramate, lamotrigine, lacosamide, clobazam, perampanel and levetiracetam only). Two blood samples will be collected: For subjects taking concomitant AEDs in the morning and coming into the visits in the morning, the first blood draw will be collected upon subjects' arrival to the study unit; the second blood draw should be collected within 30 minutes to 2 hours after the medication is taken. For patients that are taking concomitant AEDs in the afternoon and/or coming into the visits in the afternoon, the first blood draw will be collected upon subjects' arrival to the study unit; the second blood draw should be collected within 30 minutes to 2 hours after the first blood draw with timing of the dose, blood draws and strength of previous dose clearly documented.
- Record concomitant medications
- Perform drug accountability
- Record AEs
- Dispense study drug as instructed by IWRS.

- Schedule a return to occur in 2 weeks for Visit 10
- Check and dispense laminated Hypersensitivity Information safety card
- Call subject in approximately one week to check for any adverse events

9.1.10 *Visit 10, Day 113*

As shown in [Table 1](#), the following will be assessed at Visit 10:

- Record vital signs
- Perform limited physical exam for signs of hypersensitivity such as rash, swelling, lymphadenopathy and fever
- Conduct brief neurologic examination if required
- Administer C-SSRS (Since Last Visit version)
- Draw blood for laboratory safety assessment
- Record concomitant medications
- Perform drug accountability
- Record AEs
- Dispense study drug as instructed by IWRS.
- Schedule a return to occur in 4-5 weeks for Visit 11

9.1.11 *Visit 11, Day 143*

As shown in [Table 1](#), the following will be performed at Visit 11:

- Record vital signs
- Conduct brief neurologic exam if required
- Administer C-SSRS (Since Last Visit version)
- Perform urine pregnancy test (for female subjects of child-bearing potential)
- Record concomitant medications
- Perform drug accountability
- Record AEs
- Dispense study drug as instructed by IWRS.
- Schedule a return to occur in 8-9 weeks for Visit 12

9.1.12 *Visit 12, Day 203*

As shown in [Table 1](#), the following will be performed at Visit 12:

- Record vital signs
- Measure weight
- Perform brief neurologic examination if required

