- Administer C-SSRS (Since Last Visit version)
- Perform urine pregnancy test (for female subjects of child-bearing potential)
- Draw blood for laboratory safety assessment
- Record concomitant medications
- Perform drug accountability
- Record AEs
- Dispense study drug as instructed by IWRS
- Schedule a return to occur in 8-9 weeks for Visit 13

9.1.13 *Visit 13, Day 263*

As shown in [Table 1](#), the following will be performed at Visit 13:

- Record vital signs
- Conduct brief neurologic exam if required
- Administer C-SSRS (Since Last Visit version)
- Perform urine pregnancy test (for female subjects of child-bearing potential)
- Draw blood for laboratory safety assessment
- Record concomitant medications
- Perform drug accountability
- Record AEs
- Dispense study drug as instructed by IWRS.
- Schedule a return to occur in 14-15 weeks for Visit 14

9.1.14 *Visit 14 or Termination from study—Taper Visit*

As shown in [Table 1](#), the following will be performed at Visit 14 or at the time of early termination from the study.

- Record vital signs
- Measure weight
- Conduct full physical examination
- Conduct full neurologic examination
- Administer C-SSRS (Since Last Visit version)
- Perform 12-lead ECG once
- Perform urine pregnancy test (for female subjects of childbearing potential)
- Draw blood for laboratory safety assessment
- Obtain urine for urinalysis
- Record concomitant medications
- Perform drug accountability
- Record AEs
- For subjects who completed 1 year of open-label treatment, determine whether the subject is benefitting from open-label treatment with YKP3089

For subjects who are benefitting from open-label treatment:

- Dispense open-label medication
- Schedule a return to occur in 3 months for next visit
- See section [9.1.16](#) for further instructions

For subjects who are not benefitting from open-label treatment or leaving the open-label treatment due to any reasons at any time:

- Dispense taper open-label study drug bottles as instructed by IWRS if needed
- Schedule a return to occur in 2 weeks of the last dose for Visit 15 if tapered
- Schedule a return to occur in 2 weeks for Visit 15 if not tapered

9.1.15 *Visit 15, End of Study Follow-up (14 days from the last dose)*

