Visit 15 represents the Follow-up Visit after discontinuation of study drug. This final visit will take place 14 days after the subject's last dose of YKP3089—at any time during the open-label treatment or after 12 months of open-label treatment if there is no additional treatment beyond that point.

As shown in [Table 1](#), the following assessments will be performed at Visit 15:

- Record vital signs
- Measure weight
- Conduct full neurologic examination
- Administer C-SSRS (Since Last Visit version)
- Serum pregnancy test (for female subjects of child-bearing potential)
- Draw blood for laboratory safety assessment
- Record concomitant medications
- Perform drug accountability if tapered
- Record AEs

No study drug will be dispensed.

9.1.16 *Open-Label Extension Beyond Year One*

Subjects who complete Visit 14 and will continue in the open-label treatment beyond year one will adhere to the following visit schedule. The investigator will schedule a return visit in 3 months. Subjects will have study visits every 3 months for a total of 4 visits per study year. The investigator will perform some or all of the following assessments depending up on the visits.

Perform the following every 3 months from Visit 14

- Record vital signs
- Conduct brief neurologic examination if required
- Administer C-SSRS (Since Last Visit version)
- Perform urine pregnancy test (for female subjects of childbearing potential)

- Record concomitant medications
- Perform drug accountability
- Record AEs
- Dispense open-label study drug bottles as instructed by IWRS

Perform the following every 6 months from Visit 14

- Measure weight
- Draw blood for laboratory safety assessment

Perform the following every 12 months from Visit 14

- Perform full physical exam
- Perform 12-lead ECG once
- Obtain urine for urinalysis

This pattern will continue at the discretion of the investigator until development is stopped by SK Life Science Inc, the product is approved for marketing, or anytime at the discretion of SK Life Science Inc.

After the first year of open-label treatment, the visits will be numbered sequentially beginning with Visit 16.

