13.6 Columbia Suicide Symptoms and Signs Rating Scale (CSSRS)

C-SSRS Ideation, Intensity and Behavior are collected at baseline and all post-baseline visits. Summary results of response to each question (number and percentage of subjects) will be reported by safety evaluable subgroups and overall and by study visit. The summary table will include all subjects in the safety population.

At each visit, C-SSRS responses will be mapped into Columbia-Classification Algorithm of Suicide Assessment events on as follows:

- Complete suicide = as captured in the safety database (adverse events and/or reason for discontinuation)
- Suicide attempt: “Yes” on “Actual attempt” question
- Preparatory acts towards imminent suicidal behavior: “Yes” on any of the following
 - “Aborted attempt”, or
 - “Interrupted attempt”, or
 - “Preparatory acts or behavior”.
- Suicidal ideation: “Yes” on any of the following:
 - “Wish to be dead”, or
 - “Non-specific active suicidal thoughts”, or
 - “Active suicidal ideation with any methods (not plan) without intent to act”, or
 - “Active suicidal ideation with some intent to act without specific plan”, or
 - “Active suicidal ideation with specific plan or intent”.

New onset suicidality and worsening suicidality during double-blind-phase will be assessed via a shift analysis from baseline to each post-baseline visit and to any post-baseline visit. The following shift categories will be defined:

Suicidality	Baseline Event	Any post -baseline and by visit event
New onset	No suicidal ideation and no behavior (i.e., no suicide attempt or no preparatory acts towards	Any ideation (i.e., suicide ideation) or any behavior (i.e., complete suicide, suicide attempt, or

	imminent suicidal behavior)	preparatory acts towards imminent suicidal behavior)
Worsening	Suicidal ideation	Complete suicide, or suicide attempt, or preparatory acts towards imminent suicidal behavior
	Preparatory acts towards imminent suicidal behavior	Complete suicide or suicide attempt
	Suicide Attempt	Complete suicide

The number and percentages of subjects in each of the shift categories defined above will be reported by safety evaluable subgroups and overall for all subjects included in the safety population. Missing C-SSRS responses will not be imputed.

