- a. After 12 months of participation in the open-label extension phase, subjects will be re-evaluated. Those who are benefiting from treatment with YKP3089 may continue use of the drug at the discretion of the investigator, until development is stopped by SK Life Science Inc, or the product is approved for marketing, or anytime at the discretion of SK Life Science Inc.
- b. Vital signs include blood pressure, heart rate (supine for 5 minutes), temperature, and respiratory rate.
- c. Height measured only at Visit 1.
- d. Brief neurological exam should be done only if symptoms require
- e. Administer the Baseline/Screening version of the C-SSRS at Screening. Administer the Since Last Visit version at all subsequent visits.
- f. 12-lead ECG will be performed once. Additional ECGs should be performed at any other time if clinically indicated.

- g. For female subjects of childbearing potential: If pregnancy is suspected at any time during the study, an interim test may be performed in addition to scheduled assessment.
- h. Laboratory assessment: Safety assessment includes blood chemistry and hematology. If the subject meets an exclusion criterion at Visit 1, an unscheduled laboratory sampling can be repeated for confirmation.
- i. Two blood samples will be collected for the determination of YKP3089 plasma levels: For patients that are taking YKP3089 in the morning and coming into the visits in the morning, the first blood draw will be collected upon subjects' arrival to the study unit; the second blood draw should be collected within 30 minutes to 2 hours after the medication is taken. Collect at visit 8 and/ or 9 depending on stability of dosing (doses must be stable for 2 weeks prior to these visits) of all concomitant AEDs including oxcarbazepine, topiramate, lamotrigine, lacosamide, clobazam, perampanel, levetiracetam, phenytoin and phenobarbital and YKP3089. YKP3089 PK draw is applicable for subjects on phenytoin and phenobarbital globally and all subjects at US sites.

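### SAP 13.6 tabulates C-SSRS results by visit although the forms look back over anything from 14 to 102 days, with no allowance for the time covered

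*SAP*

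**What the plan says.** SAP 13.6 reports the number and percentage of subjects for each C-SSRS response by study visit. It adds that new-onset and worsening suicidality "will be assessed via a shift analysis from baseline to each post-baseline visit and to any post-baseline visit". It refers to the whole safety population, does not state the denominator for a single visit, and does not impute missing responses.

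On the form itself, SAP Appendix 1, footnote e, gives the Baseline/Screening version at screening and then instructs: "Administer the Since Last Visit version at all subsequent visits".

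The visit spacing comes from Protocol 9.1. Visits 3 to 10 are two weeks apart. The gaps then widen, as the section titles show: "Visit 10, Day 113", "Visit 11, Day 143", "Visit 12, Day 203". After Visit 13 (Day 263), Protocol 9.1.13 says "Schedule a return to occur in 14-15 weeks for Visit 14". Beyond year one, Protocol 9.1.16 says "Subjects will have study visits every 3 months for a total of 4 visits per study year".

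SAP 10.3 assigns forms to derived visits by study-day windows but does not account for how long each form looks back. SAP 11.4.1 derives subject-years, but only for drug exposure.

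**The concern.** A Since Last Visit form asks whether something happened in the interval since the previous visit. A longer interval gives more opportunity for a positive answer. The by-visit table therefore sets two-week periods beside periods of 13 to 15 weeks as if they were the same quantity.

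Suicidality is a named safety endpoint, long-term safety is a study objective, and there is no control arm to show what the schedule alone produces. SAP 10.1 plans no inferential analysis, so readers will judge time trends by eye. A step up after Visit 10 could be taken for suicidality emerging with longer treatment. A real excess in the first 16 weeks could look small beside the later columns. At the other end, Visit 15 has a shorter look-back than Visit 14 or the extension visits, so its percentage could fall for that reason alone and be read as improvement off drug.

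**Working it through.** **Inputs.** Target days are from SAP 10.3 and Protocol 9.1: 1, 15, 29, 43, 57, 71, 85, 99, 113, 143, 203, 263, 365, then 456, 547, 638, 730 and so on. The documents give no suicidality rate and no duration of ideation. Both are assumed below and varied.

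**Step 1: look-back = difference between consecutive target days, checked against the protocol's return intervals.**

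| Form | Look-back (days) | Weeks | Protocol interval |
|---|---|---|---|
| Visits 3-10 | 14 each | 2.0 | 2 weeks |
| Visit 11 | 143 - 113 = 30 | 4.3 | 4-5 weeks |
| Visit 12 | 203 - 143 = 60 | 8.6 | 8-9 weeks |
| Visit 13 | 263 - 203 = 60 | 8.6 | 8-9 weeks |
| Visit 14 | 365 - 263 = 102 | 14.6 | 14-15 weeks |
| Extension | 91-92 | about 13 | 3 months |

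The two sources agree. Two forms fall outside the pattern:
- Visit 2 looks back before dosing, by up to 21 days (Protocol 9.1.1: "Schedule Visit 2 to occur within 3 weeks of Visit 1").
- Visit 15 comes 14 days after the last dose, following a taper of 0 to 3 weeks, so it covers roughly 14 to 14 + 21 = 35 days.

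**Step 2: isolated events at a constant rate.** With subjects assessed as the denominator, P(T) = 1 - exp(-rate × T / 365.25).

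| Assumed rate per 100 subject-years | 14 days | 30 days | 60 days | 102 days | 91 days |
|---|---|---|---|---|---|
| 1 | 0.04% | 0.08% | 0.16% | 0.28% | 0.25% |
| 5 | 0.19% | 0.41% | 0.82% | 1.39% | 1.24% |
| 10 | 0.38% | 0.82% | 1.63% | 2.75% | 2.46% |

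The ratio to a 14-day form is about 2.1 at 30 days, 4.3 at 60 and 6.5 at 91. At 102 days it is 7.28 for a rate of 1 per 100 subject-years and 7.11 for a rate of 20. It hardly depends on the rate, because it is close to 102/14 = 7.3.

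SAP 15.1 prints percentages to one decimal. At 5 per 100 subject-years the table would show 0.2% at Visits 3-10 and 1.4% at Visit 14, so the effect would not be lost in rounding.

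**Step 3: persisting ideation.** If episodes last D days on average, the chance of a positive form is roughly proportional to 1 + T/D. The ratio of a 102-day to a 14-day form is then (D + 102)/(D + 14).
- D = 14: 116/28 = 4.1
- D = 30: 132/44 = 3.0
- D = 90: 192/104 = 1.8 to 1.9 (1.846)
- D = 365: 467/379 = 1.2

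The direction does not change, but the size depends heavily on D.

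**Step 4: shape.** The expected percentage is flat over Visits 3-10, steps up to Visit 14, then drops by (1.387 - 1.238)/1.387 = about 11% to a plateau.

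**Step 5: does dividing by time covered remove the effect?** At a true 5 per 100 subject-years, P(T)/T gives 5.00, 4.99, 4.98, 4.97 and 4.97 per 100 subject-years for 14-, 30-, 60-, 102- and 91-day forms. It does, to within 1%.

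**Step 6: actual against scheduled look-back.** Visit windows are ±2 days for Visits 3-10 and ±7 days for other open-label visits. Early look-backs can therefore run from about 10 to 18 days, and Visit 14 from 102 - 14 = 88 to 102 + 14 = 116. Missed visits lengthen them further.

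**The case against.** The strongest reply has four parts.

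1. **A rise is not guaranteed.** It needs constant risk and a denominator of subjects assessed, and SAP 13.6 states no by-visit denominator. If the whole safety population is used, dropout and an early data cut-off (SAP 14) pull later percentages down. Retention of 14/102, about 14%, at Visit 14 would cancel the effect for isolated events. About 81% (1/1.23) would cancel it for 365-day episodes. This stands. It does not rescue the table, since an unstated denominator adds a second distortion and does not correct the first.

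2. **Seven-fold is an upper bound.** The by-visit table counts anyone positive at that visit, so persisting ideation recurs in column after column and shrinks the ratio. This stands.

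3. **Timing is available elsewhere.** Adverse event onset day is derived. Deaths, serious events and discontinuations are listed with dose at onset and study day. Completed suicide comes from the safety database. This stands in part, because listings do not summarise C-SSRS ideation over time and the by-visit table is the only planned C-SSRS summary that does.

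4. **Dose comparisons within titration are sound.** The steps from 12.5 to 200 mg/day fall in Weeks 1-12, where every on-treatment form covers 14 days. This stands. Only later dose changes can overlap with the longer look-backs.

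The any-post-baseline shift is also cumulative and has no unequal-window comparison between visits, although it depends on total follow-up.

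**Conclusion.** The point holds in a limited form. The look-back lengths are exact at target days, the SAP reports by visit, and it makes no allowance for time covered. At equal underlying risk among subjects assessed, the later columns are inflated relative to Visits 3-10. At Visit 14 the factor is up to about 7 for isolated events and falls to about 1.2 for year-long episodes. These factors rest on an assumed constant rate (1 to 20 per 100 subject-years) and assumed episode lengths (14 to 365 days).

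A reader might infer that the by-visit percentages must rise with time on drug, or that a seven-fold increase should be expected. The documents support neither. They do not state the denominator or give a rate or episode length, and observed values could be flat or fall. Even under constant risk, the pattern is a step and then a plateau, not a continuing climb. The any-post-baseline result is not affected in this way. What is affected is the reading of C-SSRS results over time. It merits a cheap correction before the tables are produced.

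**What to change.** In SAP 13.6:

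1. **Add a by-period table**, for example Day 1-113, Day 114-365 and each later year. The numerator is first-ever treatment-emergent new-onset or worsening suicidality. The denominator is subject-years at risk: the time covered by completed forms, from actual form dates, censored at the first event. State the rule that assigns each form to a period, for example by form date. First-ever counting matters. If the first positive form within each period were counted, a subject with continuous ideation would contribute one event per 113/365.25 = 0.31 years in the first period and one per 252/365.25 = 0.69 years in the second. That is a false decline of about 2.2-fold.

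2. **Keep the by-visit table**, with subjects assessed at that visit as the denominator and n shown. Print the median and range of actual days covered in each column. Scheduled lengths would mislead, because the analysis windows are wide (Visit 14 takes Days 315 to 410) and absorb unscheduled and termination visits. Footnote that columns with different look-back lengths are not directly comparable.

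The cost is SAP wording, one extra derivation (days covered per form, with the assignment rule) and one extra table. Form dates are already collected, so no new data are needed.

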10.3 Visit Windows for Safety Analyses

The table below presents the visits assigned for safety analyses corresponding to the range of treatment study days (window) during which an actual visit (scheduled or unscheduled) may occur. Note that the windows defined for statistical analysis are different from the ones defined in Protocol Section 9.

Visit windows for laboratory tests, vital signs, and for Columbia Suicide Symptoms and Signs Rating Scale (CSSRS):

Derived Visit	Target Study Day [1]	Window [2]
Baseline (for laboratory tests and vitals)	Day 1	Days <= 1
Baseline (for C-SSRS)	Screening (Visit 1)	NA
Visit 2 (for C-SSRS)	Day 1	Days = 1
Visit 3	Day 15	>= Day 2 to <= Day 22
Visit 4	Day 29	>= Day 23 to <= Day 36

Visit 5	Day 43	>= Day 37 to <= Day 50
Visit 6	Day 57	>= Day 51 to <= Day 64
Visit 7	Day 71	>= Day 65 to <= Day 78
Visit 8	Day 85	>= Day 79 to <= Day 92
Visit 9	Day 99	>= Day 93 to <= Day 106
Visit 10	Day 113	>= Day 107 to <= Day 128
Visit 11	Day 143	>= Day 129 to <= Day 173
Visit 12	Day 203	>= Day 174 to <= Day 233
Visit 13	Day 263	>= Day 234 to <= Day 314
Visit 14	Day 365	>= Day 315 to <= Day 410
3 Months after 1 Year Treatment	Day 456	>= Day 411 to <= Day 501
6 Months after 1 Year Treatment	Day 547	>= Day 502 to <= Day 592
9 Months after 1 Year Treatment	Day 638	>= Day 593 to <= Day 684
12 Months after 1 Year Treatment	Day 730	>= Day 685 to <= Day 775
15 Months after 1 Year Treatment	Day 821	>= Day 776 to <= Day 866
18 Months after 1 Year Treatment	Day 912	>= Day 867 to <= Day 957
21 Months after 1 Year Treatment	Day 1003	>= Day 958 to <= Day 1049
24 Months after 1 Year Treatment	Day 1095	>= Day 1050 to <= Day 1112
Visit 15 (14-day follow-up)	Day of the last dose of study	>= day of the last dose of study drug+14

	drug+14 days	
Termination Visit [3]	Termination Visit during treatment period	

[1] Relative to the date of the first dose of study drug. For example, Day 1 = the date of the first dose of study drug.

[2] The study days evaluated for windows of visits during treatment period are on or prior to the last dose day.

[3] For subjects who decide not to continue in the study at any time (i.e., eCRF check box for “Continuing” is answered ‘No’), the Termination Visit is performed (as per Protocol Section 9.1.14). This is available for entry at any time as a separate visit on eCRF. The study day for the termination visit will be assigned relative to the first dose of study drug.

Visit windows for ECG measurements:

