Derived Visit	Target Study Day [1]	Window [2]
Baseline	Day 1	Days <= 1
Visit 14	Day 365	>= Day 2 to <= Day 547
12 Months after 1 Year Treatment	Day 730	>= Day 548 to <= Day 914
24 Months after 1 Year Treatment	Day 1095	>= Day 915 to <= Day 1112
Visit 15 (14-day follow-up)	Day of the last dose of study drug+14 days	>= day of the last dose of study drug+14
Termination Visit [3]	Termination Visit during treatment period	

[1] Relative to the date of the first dose of study drug. For example, Day 1 = the date of the first dose of study drug.

[2] The study days evaluated for windows of visits during treatment period are on or prior to the last dose day.

[3] For subjects who decide not to continue in the study at any time (i.e., eCRF check box for “Continuing” is answered ‘No’), the Termination Visit

is performed (as per Protocol Section 9.1.14). This is available for entry at any time as a separate visit on eCRF. The study day for the termination visit will be assigned relative to the first dose of study drug.

Visit windows for Physical Exam measurements:

Derived Visit	Target Study Day [1]	Window [2]
Baseline	Day 1	Days <= 1
Visit 3	Day 15	>= Day 2 to <= Day 22
Visit 4	Day 29	>= Day 23 to <= Day 36
Visit 5	Day 43	>= Day 37 to <= Day 50
Visit 6	Day 57	>= Day 51 to <= Day 64
Visit 7	Day 71	>= Day 65 to <= Day 78
Visit 8	Day 85	>= Day 79 to <= Day 92
Visit 9	Day 99	>= Day 93 to <= Day 106
Visit 10	Day 113	>= Day 107 to <= Day 239
Visit 14	Day 365	>= Day 240 to <= Day 547
12 Months after 1 Year Treatment	Day 730	>= Day 548 to <= Day 914
24 Months after 1 Year Treatment	Day 1095	>= Day 915 to <= Day 1112
Visit 15 (14-day follow-up)	Day of the last dose of study drug+14 days	>= day of the last dose of study drug+14
Termination Visit [3]	Termination Visit during treatment period	

[1] Relative to the date of the first dose of study drug. For example, Day 1 = the date of the first dose of study drug.

[2] The study days evaluated for windows of visits during treatment period are on or prior to the last dose day.

[3] For subjects who decide not to continue in the study at any time (i.e., eCRF check box for “Continuing” is answered ‘No’), the Termination Visit is performed (as per Protocol Section 9.1.14). This is available for entry at any time as a separate visit on eCRF. The study day for the termination visit will be assigned relative to the first dose of study drug.

Visit Day is calculated by (Visit date – date of the first dose of study drug + 1).

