10.4 Baseline Value and Change from Baseline

For all safety variables that involve eCRF data collected during study visits prior to the first dose of study drug, the baseline value is defined as the last non-missing value obtained immediately prior to the first dose.

Change from baseline variables will be calculated by subtracting the baseline value from the post-baseline derived visit (i.e., for derived Visit 3 to Visit 15 as per table in [Section 11.4](#)) for each subject.

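### The SAP gives two C-SSRS baselines and reconciles neither: ideation first recorded before dosing can count as new onset, and a next-morning first dose leaves Visit 2 in no C-SSRS window

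*SAP*

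**What the plan says.** SAP 13.6 defines new onset as no ideation or behavior at baseline followed by any ideation or behavior later, "assessed via a shift analysis from baseline to each post-baseline visit and to any post-baseline visit". It names no baseline visit and cites neither 10.3 nor 10.4. By contrast, 13.2 to 13.4 each define their baseline and refer to 10.3.

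Two other sections bear on the choice:

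- **SAP 10.3.** The row "Baseline (for C-SSRS") is set at Screening (Visit 1) with no day window. A separate row, "Visit 2 (for C-SSRS"), has the window Days = 1, and Visit 3 begins at Day 2. The row "Baseline (for laboratory tests and vitals") has the window Days <= 1. The study-day rule reads "Visit Day is calculated by (Visit date – date of the first dose of study drug + 1").
- **SAP 10.4.** The general rule covers every safety variable with eCRF data from visits before dosing, which takes in the C-SSRS at Visits 1 and 2. Under it, "the baseline value is defined as the last non-missing value obtained immediately prior to the first dose". There is no C-SSRS exception. Change from baseline is taken at each "post-baseline derived visit (i.e., for derived Visit 3 to Visit 15").

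SAP 8.1 and 8.2.2 place the baseline form at Visit 1 and the follow-up form from Visit 2 onward, both entered on the eCRF. Protocol 9.1.1 schedules Visit 2 within 3 weeks of Visit 1. Under Protocol 9.1.2, drug is first dispensed at Visit 2, any dose given at the clinic comes after the other Visit 2 procedures, and the subject may instead take the first dose the following morning.

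**The concern.** The Visit 2 C-SSRS uses the Since Last Visit form and covers up to three weeks without drug. It is pre-treatment information. Taking Visit 1 alone as baseline ignores it; taking Visit 2 alone ignores Visit 1. Either way, ideation already recorded before the first dose can reappear as new onset on treatment.

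The C-SSRS is a named safety endpoint in a single-arm, descriptive study, so the new-onset count will be read without a comparator. The adverse-event rule in SAP 13.1 is stricter: an event that began before dosing is treatment-emergent only if it worsened afterwards.

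The independent programming required by SAP 15.2 could show that two programmers read the baseline differently, but could not say which is right. It would not reveal the problem within 10.3 at all, since both could follow that rule correctly.

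The Day 0 gap is a separate fault. It removes a valid pre-dose assessment from tables that SAP 15.1(a) ties to the derived visits.

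**Working it through.** The plan states no figure here, so there is none to reproduce. The check applies the written rules to the possible cases.

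**Step 1: study day of Visit 2.** Formula (SAP 10.3): visit date − first dose date + 1.

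- First dose on the day of Visit 2: 0 + 1 = Day 1. This is inside the C-SSRS Visit 2 window (Days = 1).
- First dose the next morning: −1 + 1 = Day 0. Visit 2 requires Day 1, Visit 3 starts at Day 2, and the C-SSRS baseline row has no window, so no C-SSRS window holds it. The laboratory and vital-signs baseline (Days <= 1) does.

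**Step 2: new-onset scoring.** Take ideation at Visit 1, pre-dose Visit 2 and Visit 3 (N = absent, Y = present). There are 2 × 2 × 2 = 8 patterns. New onset, by SAP 13.6, is N at baseline and Y at any post-baseline visit.

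| Pattern | A: 10.3 baseline (Visit 1), post-baseline from Visit 3 | B: 10.4 baseline (Visit 2), post-baseline from Visit 3 | C: 10.3 baseline, Visit 2 post-baseline, same-day dose | Any pre-dose Y counts as baseline ideation |
|---|---|---|---|---|
| NNN | no | no | no | no |
| NNY | yes | yes | yes | yes |
| NYN | no | no | yes | no |
| NYY | yes | no | yes | no |
| YNN | no | no | no | no |
| YNY | no | yes | no | no |
| YYN | no | no | no | no |
| YYY | no | no | no | no |
| Total yes | 2 | 2 | 3 | 1 |

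The last column takes a Visit 1 yes as falling within the stated recall period.

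**Step 3: comparison.**

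- A against B: NYY and YNY differ, so 2 of 8.
- A, B and C together, same-day dose: NYN, NYY and YNY differ, so 3 of 8.
- With a next-morning dose, Visit 2 has no window and C scores only NNY and NYY, the same as A. The difference is again 2 of 8.

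**Step 4: what each disagreement means.** NYY is new onset under 10.3 whether or not Visit 2 counts as post-baseline, although the ideation was first recorded before dosing. The recall period of the Visit 1 form does not matter here, because the Visit 1 answer is no. YNY is new onset only under 10.4; whether it should be depends on that recall period, which the documents available do not show.

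**The case against.** The strongest reply is that the specific rule governs the general one. The 10.3 row is the only baseline written for the C-SSRS. It agrees with SAP 8.1 and with the Appendix 1 flowchart, which labels Visit 1 the safety baseline. The SAP revision history says version 3.0 clarified the C-SSRS windows. On this view a cross-reference is missing and little else. This is a reasonable reading and probably what was intended, but the SAP never states the precedence, and granting it leaves NYY scored as new onset.

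A second reply is that NYY is a deliberate, conservative choice: it over-counts a safety signal, as SAP 13.1 does by treating missing severity as severe. The direction is right for this pattern, and with same-day dosing the Visit 2 row would still show the earlier ideation. But the SAP gives no such rationale, and with next-morning dosing that row is lost. The by-subject listings would still hold the record.

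A third reply is that few subjects may be affected. Subjects are dosed only if they still meet eligibility at Visit 2. The exclusion list in the available text stops at item 7, while Protocol 8.4 refers to vigabatrin and ezogabine criteria that are not among those items. A suicidality exclusion may exist and would thin out NYY. This stands as a limit on size.

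Finally, pooling all pre-dose answers could remove genuine on-treatment recurrence from new onset if the Visit 1 form has long recall. That also stands, and the remedy must therefore state the recall period.

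**Conclusion.** The concern holds. Sections 10.3 and 10.4 point to different C-SSRS baselines, and 13.6 settles neither the baseline nor the status of Visit 2. The rules as written classify 2 of 8 ideation patterns differently. This becomes 3 of 8 only if Visit 2 is treated as post-baseline and dosing is same-day. These are unweighted patterns, not an effect size. The clearest fault is NYY, which the more specific rule scores as new onset despite a pre-dose record.

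The Day 0 gap also holds. With a Visit 1 baseline it loses the Visit 2 row; it does not by itself create false new onset.

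The number of subjects affected cannot be computed, because the documents give neither C-SSRS rates nor the share dosing the next morning. The conclusion assumes that the Visit 2 C-SSRS is completed before the first dose, as Protocol 9.1.2 implies. The point should be corrected, but it concerns a descriptive safety table and does not threaten the study as a whole.

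**What to change.** - In SAP 10.3, 10.4 and 13.6, state one C-SSRS baseline that uses all pre-dose assessments (Visit 1 and the pre-dose Visit 2). Say which Visit 1 responses and which recall period count.
- Define post-baseline for the C-SSRS as after the first dose, from derived Visit 3 onward, and state that this rule overrides 10.4 for this scale.
- Change the C-SSRS Visit 2 window from Days = 1 to Day 0 or Day 1, pre-dose.

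Subjects with pre-dose ideation who later show suicidal behavior would still appear under the existing worsening category. An extra row for movement to a higher ideation item (1 to 5) would be a useful option but is not needed to correct the fault.

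Two editorial slips can be corrected in the same revision: 13.6 refers to a double-blind phase in an open-label study, and 10.4 points to Section 11.4 for a visit table that is in 10.3.

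The cost is SAP wording and minor reprogramming of one baseline and one window, with no new data collection. SAP section 4 allows revision before database lock.
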